9.3 Handling of Multiplicity

There is no statistical testing, and therefore multiplicity adjustment is not applicable.

9.4 Efficacy Variables Definitions and Conventions

9.4.1 ACR Criteria

ACR criteria are a commonly used standard criteria set mentioned in the guidance of American College of Rheumatology and US FDA to evaluate the effectiveness of investigational drug in RA clinical trials. It is a composite measurement calculated based on the improvement over a set of core measurements.

ACR20 is defined as at least 20% improvement (compared to baseline values) in tender and swollen joint counts and at least 20% improvement in 3 of the remaining 5 core set measures (subject global assessment of pain, subject global assessment of disease activity, physician global assessment of disease activity, subject assessment of physical function and acute phase reactant hsCRP).

ACR50 and ACR70 are similarly defined with at least 50% and 70% improvement, respectively.

A subject will be classified as an ACR20 (ACR50, ACR70) responder, if the following conditions are met:

1. $\geq 20\%$ (50%, 70%) improvement from baseline in tender joint count (TJC68) and
2. $\geq 20\%$ (50%, 70%) improvement from baseline in swollen joint count (SJC66) and
3. $\geq 20\%$ (50%, 70%) improvement from baseline in at least 3 of the following 5:
 - Patient's assessment of pain
 - Patient's global assessment of disease activity (PGA)
 - physician's global assessment of disease activity (PhGA)
 - patient's self-assessment of physical function (i.e., measured by Health Assessment Questionnaire (HAQ-DI score))
 - Acute-phase reactant value hsCRP/ESR

The following table illustrates examples for As Observed ACR calculations.

Example	TJC 68	SJC 66	Component 1	Component 2	Component 3	Component 4	Component 5	ACR20- Response?
A	1	1	1	1	1	.	.	Yes
B	1	0	1	1	1	1	1	No
C	.	0	No
D	1	.	1	1	1	1	1	.
E	1	1	0	0	0	1	1	No
F	.	.	0	0	0	.	.	No
G	1	1	1	1	0	0	.	.

Legend: 1 = $\geq 20\%$ improved compared to baseline; 0 = $< 20\%$ improved compared to baseline; "." Missing

Windowing Rule for ACR Response Calculation:

- ACR component values will first be determined at each date within a visit window.
- ACR component values at each date will be combined to determine the observed ACR composite score at each date in each window.
- After this calculation, if multiple non-missing ACR composite scores are available within a given visit window, the non-missing ACR composite score closest to the target day will be used. If two composite scores have the same distance from the target day, the later one will be used. The corresponding date will be used as the observed ACR response date in the derived efficacy dataset.
- If a non-missing ACR composite score is not available for any day within a given visit window, the windowed component values for that visit will be used to calculate the ACR composite score for that visit window (component value windowing follow the same rules as in steps described above). The date of observed ACR composite score will be determined by the first available ACR component date, in the order of TJC, SJC, Pain, PGA, PhGA, HAQ-DI, CRP/ESR, in the derived efficacy dataset.

9.4.2 Joint Evaluation

Anatomical joints are evaluated for swelling and tenderness at every study visit. The 34 anatomical joints in [Table 3](#) are assessed in this study for both the left and right side of the body.

Table 3. Anatomical Joints Assessed for Calculation of Tender and Swollen Joint Counts (TJC68 and SJC66)

Temporomandibular	Sternoclavicular	Acromio-clavicular	Shoulder
Elbow	Wrist	Metacarpophalangeal I	Metacarpophalangeal II
Metacarpophalangeal III	Metacarpophalangeal IV	Metacarpophalangeal V	Thumb Interphalangeal
Proximal Interphalangeal II	Proximal Interphalangeal III	Proximal Interphalangeal IV	Proximal Interphalangeal V
Distal Interphalangeal II	Distal Interphalangeal III	Distal Interphalangeal IV	Distal Interphalangeal V
Hip ^a	Knee	Ankle	Tarsus
Metatarsophalangeal I	Metatarsophalangeal II	Metatarsophalangeal III	Metatarsophalangeal IV
Metatarsophalangeal V	Great Toe/Hallux	Interphalangeal II	Interphalangeal III
Interphalangeal IV	Interphalangeal V		

a. Hip joints are not assessed for swelling.

At each study visit, a joint evaluator assessed whether a particular joint was "tender or painful" where presence of tenderness was scored as "1" and the absence of tenderness was scored as "0," provided the joint was not replaced ("9") or could not be assessed ("NA") due to other reasons (e.g., post-corticosteroid joint injection). The total tender joint count (TJC68), which is based on 68 joints, will be derived as the sum of all "1s" thus collected and no penalty will be considered for the joints not assessed or those which have been replaced. A similar method will be followed for the derivation of total swollen joint count (SJC66), which is based on 66 joints as the hip joints are excluded. Thus, the range for TJC68 will be 0 to 68 and 0 to 66 for SJC66.

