### **Treatment Period**

The treatment period for OLE can begin immediately after or up to 30 days following the Last Visit (Week 12) of Study M13-550 or Study M13-537 RCT and will continue for approximately 312 weeks in OLE. At Last Visit (Week 12) or up to 30 days following the Last Visit (Week 12) of Study M13-550 or Study M13-537, subjects who meet all the inclusion criteria and none of the exclusion criteria described in Section 5.2.1 and Section 5.2.2 will be enrolled into the study. Subjects will visit the study site at Weeks 6, 12, 18 (Optional), 24, 36, 48, 60, 72, 84, 96 and every 12 weeks thereafter until the end of the study or if they terminate early from the study. A  $\pm$  7-day window is permitted around scheduled study visits. The last dose of study drug is taken the evening prior to the final visit.

Subjects may discontinue study drug treatment at any time during study participation. Subjects that end study participation early will have a Premature Discontinuation Visit and complete the procedures outlined for Premature Discontinuation Visit in Table 2 as soon as possible, preferably within 2 weeks of study drug discontinuation and preferably prior to initiation of another therapy.

Starting with Amendment 5, subjects who are receiving 30 mg QD open-label upadacitinib will have the option to decrease to the 15 mg QD dose based on investigator's discretion.

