### 5.2.3 Prior and Concomitant Therapy

Any medication or vaccine (including over-the-counter or prescription medicines, vitamins and/or herbal supplements including folic acid) that the subject is receiving at the time of enrollment, or receives during the study, must be recorded along with the reason for use, date(s) of administration including start and end dates, and dosage information including dose, route and frequency on the appropriate eCRF.

Subjects should remain on a stable dose of MTX throughout the first 24 weeks of Study M13-538. However, if a subject experiences MTX-induced toxicity, MTX dose can be reduced or discontinued as per Investigator's medical judgment.

After 24 weeks of treatment with open-label upadacitinib, initiation of or change in a subject's concomitant medications for RA, including MTX and other csDMARDs or corticosteroids (oral or parenteral) is allowed.

Stable doses of non-steroidal anti-inflammatory drugs (NSAIDs), acetaminophen, or oral corticosteroids (equivalent to prednisone  $\leq 10$  mg) are allowed throughout the study. PRN use of NSAIDs, acetaminophen, tramadol, codeine, propoxyphene and hydrocodone is allowed except 24 hours prior to any study visit.

Intra-articular, intra-muscular, intra-bursa and intra-tendon sheath injections of corticosteroids, dosage and frequency per standard of care, are allowed during the study. Details of each injection, along with the name of the joint injected, must be captured on appropriate eCRF as mentioned above. Subjects should have their joint(s) scored prior to receiving the injection. Any injected joints will be scored as "**NA = no assessment**" for 90 days from the time of injection.

The AbbVie Therapeutic Area Medical Director identified in Section 6.8 (Adverse Event Reporting) should be contacted if there are any questions regarding concomitant or prior therapy(ies).

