#### **Swollen Joint Count (SJC)**

An assessment of 66 joints ([Appendix C](#)) will be done by directed physical examination at visits specified in [Table 2](#). The joints to be examined for swelling are the same as those

examined for tenderness, except the hip joints are excluded. Joint swelling will be classified as present ("1"), absent ("0"), replaced ("9") or no assessment ("NA").

If a patient receives an intra-articular injection during the study, the injected joint(s) should be scored as "NA = no assessment" for 90 days following injection.

If possible, the TJC and SJC should be performed by an independent joint assessor who should not perform any other study related procedures, as much as possible. In order to minimize variability, the same independent joint assessor should evaluate the subject at each visit for the duration of the trial. A back-up independent assessor, who is trained and competent in performing such assessments, should be identified. It is the responsibility of the Principal Investigator to ensure all assessors are qualified to perform joint assessments and that all training is documented. If the independent assessor is not available, the pre-identified back-up assessor will perform such assessments.

Due to a state of emergency or pandemic situation like COVID-19, subject visits may be conducted via phone or video conference. In these situations, the TJC and SJC will be performed at the next feasible visit by the independent joint assessor, if possible.

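### A joint injected with corticosteroid during the extension is counted as inactive while it is not assessed, which can only flatter that subject's response

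*SAP*

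**What the plan says.** SAP 9.4.2 (Joint Evaluation) scores each joint 1 or 0 unless it is replaced (9) or not assessable (NA), and itself gives a recent steroid injection as an example of NA. The tender joint count "will be derived as the sum of all '1s' thus collected". For joints scored NA or 9, the same sentence makes no adjustment of any kind: "no penalty will be considered for the joints not assessed or those which have been replaced". The swollen count follows the same method.

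Protocol 5.2.3 lets local steroid use run freely: "injections of corticosteroids, dosage and frequency per standard of care, are allowed during the study". Protocol 5.3.1.1 (Swollen Joint Count) then requires that "the injected joint(s) should be scored as 'NA = no assessment' for 90 days following injection", and 5.2.3 repeats the 90-day rule. Section 5.2.3 also says that "Subjects should have their joint(s) scored prior to receiving the injection" and asks for the name of the injected joint on the eCRF.

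On timing, Protocol 5.1 (Treatment Period) states: "Subjects will visit the study site at Weeks 6, 12, 18 (Optional), 24, 36, 48, 60, 72, 84, 96 and every 12 weeks thereafter", with a window of plus or minus 7 days. SAP 5.2 fixes baseline at the last value on or before the first dose in the parent trial.

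The SAP has no carry-forward, proration or minimum number of assessed joints for these counts. Its rules for missing components (9.4.1, 9.4.6 to 9.4.8) act when a whole component is missing, and a count containing NA joints is not missing. By contrast, HAQ-DI (9.4.10) is divided by the categories answered and FACIT-Fatigue (9.4.11) is prorated.

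**The concern.** Joints are injected because they are active. Under the SAP rule, an injected joint goes from adding 1 to adding 0 without anyone having examined it, while the baseline count still contains it. The subject appears to improve because of the coding. If the steroid really did quiet the joint, the count credits study drug with a local treatment effect.

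The 68/66-joint counts feed ACR20/50/70, and the 28-joint counts feed DAS28 (CRP), CDAI and SDAI and the LDA and remission rates built on them. Most of the efficacy results of this extension therefore pass through the rule. A joint replaced after baseline acts in the same way on percent improvement.

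**Working it through.** **The plan's own figure.** SAP Table 3 lists 34 joints on two sides: 34 × 2 = 68 tender joints, less 2 hips = 66 swollen. The stated ranges, 0 to 68 and 0 to 66, reproduce.

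**How often a visit is affected.** Target days are 84 days apart from Week 12 (SAP Table 1).

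- An injection d days after a visit (d = 0 to 83, given after scoring) reaches the next visit 84 − d days later, which is always within 90 days.
- It reaches the following visit within 90 days if 168 − d ≤ 90, that is d ≥ 78. So 78 of the 84 days blank one visit and 6 blank two.
- An injection on Day 1 blanks both Week 6 (42 days later) and Week 12 (84 days later).
- The window can stretch a gap to 84 + 7 + 7 = 98 days. Since 98 − 90 = 8, an injection 0 to 7 days after such an early visit is then missed by the NA period. Most injections blank a visit, but not all.

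**Effect on percent improvement.** Protocol 8.1.5.1 gives (baseline − current) / baseline × 100. One active joint is injected. Proration multiplies the visit count by N/(N − 1), with N = 66 (68 in the last row).

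| Baseline | Active before injection | SAP rule | Pre-injection score kept | Prorated |
|---|---|---|---|---|
| 8 | 7 | 25.0% | 12.5% | 23.8% |
| 10 | 9 | 20.0% | 10.0% | 18.8% |
| 10 | 6 | 50.0% | 40.0% | 49.2% |
| 10 | 4 | 70.0% | 60.0% | 69.5% |
| 20 | 17 | 20.0% | 15.0% | 18.8% |

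Each injected active joint adds 100/baseline points. Proration removes little of this, because it treats the injected joint as a random one.

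**Effect on the indices.** If the joint is one of the 28 and both tender and swollen, CDAI falls by 2. DAS28 falls by 0.56(√T − √(T−1)) + 0.28(√S − √(S−1)), where T and S are the 28-joint tender and swollen counts. That is 0.35 at T/S = 2/2, 0.24 at 4/3 and 0.19 at 6/4. It reaches 0.84 only if this is the subject's sole active joint.

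**Cases that behave differently.**

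- Replaced before baseline: the joint adds 0 at both times, so percent improvement is unchanged.
- NA at baseline, assessed later: a true change from 10 to 8 (20.0%) is recorded as 9 to 8, (9 − 8)/9 = 11.1%. Here the bias runs against response.
- Replaced after baseline: with baseline 8 and 6 other joints active, the SAP rule gives 25.0%. Dropping the joint from both counts gives (7 − 6)/7 = 14.3%.

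**Overall size, on assumed inputs.** The documents give neither injection frequency nor baseline counts. A simulation of the joint-count part of ACR took mean baseline TJC/SJC of 15/10 or 25/16 (minimum 6 each), a beta(0.8, 1.6) fraction of joints still active (tender joints 1.1 times as likely to persist), and one or two injected joints, each tender and swollen. The rise in response among affected subjects, in percentage points, against keeping the pre-injection score, is:

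| Mean TJC/SJC | Injected joints | 20% | 50% | 70% |
|---|---|---|---|---|
| 15/10 | 1 | 6.8 | 9.7 | 11.2 |
| 15/10 | 2 | 15.5 | 22.0 | 22.7 |
| 25/16 | 1 | 4.0 | 5.8 | 7.2 |
| 25/16 | 2 | 8.4 | 12.8 | 15.0 |

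Multiplying the smallest (4.0) and largest (22.7) by the share of subjects affected at a visit gives 0.1 to 0.5 points overall at 2%, 0.4 to 2.3 at 10% and 0.8 to 4.5 at 20%.

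**The case against.** The best defence is that the rule is open and pre-specified in a descriptive, single-arm study without tests, and that SAP 9.1.1 rules out imputation. Carrying an active score for 90 days assumes that neither drug nor steroid helped, which errs the other way. It also does not isolate study drug, because csDMARDs and other steroids may be started or changed after Week 24 and their effects stay in the observed data. The pre-injection score may not always exist: the electronic device takes entries only at protocol visits (Protocol 10.2), and the joint worksheet gives no reason for NA.

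Much of this stands. It is why both rules should be reported, and why a fallback is needed when no pre-injection score was captured. It does not rescue the rule itself. Adding 0 for an unexamined joint is already an imputation, and the most favourable one. With systemic treatment changes the joint is at least still examined.

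A reader might infer more than the documents support: that the whole NA and replaced-joint rule inflates response, or that every injection blanks a visit. Joints NA at baseline, joints replaced before baseline and the 98-day gap show otherwise. Nor does every joint-count crossing become an ACR response. Both counts and 3 of 5 other measures must also meet the threshold.

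**Conclusion.** The point holds for active joints injected during the extension and, for percent improvement, for active joints replaced after baseline. Compared with using the joint's pre-treatment state, the SAP rule can only leave response unchanged or raise it; for injected joints it can likewise only lower DAS28, CDAI and SDAI or leave them unchanged. The direction follows from the text. The size does not: it depends on injection frequency, and the figures of 0.1 to 0.5 points (2% affected) and 0.8 to 4.5 points (20% affected) rest on the assumed inputs above and precede the 3-of-5 condition. A small overall effect is the likely case, and the documents do not support a claim that the published response rates would be materially wrong. The change is worth making because the direction is known and the correction is cheap.

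**What to change.** In SAP 9.4.2:

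1. For a joint that is NA because of a post-baseline injection (identified from the injection eCRF), use its pre-injection tenderness and swelling scores during the NA period, or its last recorded scores if none were captured. Apply this to the 68/66-joint and 28-joint counts.
2. For a joint replaced after baseline, drop it from both the baseline and the visit count, for percent improvement only. Absolute DAS28 and CDAI cut-offs are unaffected by dropping it, since it already adds 0 at the visit.
3. Report results under the current rule alongside, and tabulate by visit the number of subjects with NA or newly replaced joints.

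The cost is SAP wording and programming, including linking NA joints to the names and dates on the injection eCRF. Response rates become slightly less favourable, and the carried score may overstate activity where the joint truly improved, which the side-by-side results will show. No change is proposed to the dosing or discontinuation rules that use joint counts.

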9.4.3 Patient's Global Assessment of Disease Activity Visual Analog Scale (VAS)

The subject will assess his/her disease activity for the past 24 hours using a Patient's Global Assessment of Disease VAS. The range is 0 to 100 mm with no activity being indicated by 0 and severe activity by 100.

9.4.4 Physician's Global Assessment of Disease Activity Visual Analog Scale (VAS)

The physician will assess Patient's disease activity at the time of visit using a Physician's Global Assessment of Disease VAS. The range is 0 to 100 mm with no activity being indicated by 0 and severe activity by 100.

9.4.5 Patient's Global Assessment of Pain

The subject will assess his/her pain in the previous week using a Patient's Global Assessment Pain VAS. The range is 0 to 100 mm with no pain being indicated by 0 and severe pain by 100.

9.4.6 Disease Activity Score Based on CRP (DAS28 [CRP])

DAS28 (CRP) is a composite index to assess disease activity in RA patients using hsCRP measurement. The DAS provides a score between 0 and 10, indicating how active the rheumatoid arthritis is at the time of measurement.

It can be calculated based on Tender Joint Count, Swollen Joint Count, Patient's Global Assessment of Disease Activity (PtGA) (in mm), and hsCRP (in mg/L).

$$\text{DAS28 (CRP)} = 0.56 \times \sqrt{\text{TJC28}^*} + 0.28 \times \sqrt{\text{SJC28}^{**}} + 0.36 \times \ln(\text{hsCRP}^{\&} + 1) + 0.014 \times \text{PtGA}^{\gg} + 0.96$$

* TJC28 refers to the Subject's total Tender Joint Count out of the provided 28 evaluated joints.

** SJC28 refers to the Subject's total Swollen Joint Count out of the provided 28 evaluated joints.

& hsCRP refers to the high-sensitivity c-reactive protein lab value. hsCRP unit in the DAS28 (CRP) equation is expressed as mg/L.

ESR refers to the Erythrocyte sedimentation rate. ESR unit in the DAS28 (ESR) equation is expressed as mm/hr.

» PtGA refers to the Patient's Global Assessment of Disease Activity.

where $\sqrt{\quad}$ is square root and \ln is natural log.

TJC28 and SJC28 represent total tender joint count and total swollen joint count, respectively, based on the 28 joints (including the left and right side of the body) listed in the table below.

Table 4. Anatomical Joints for DAS28 (CRP) Calculation

Shoulder	Elbow	Wrist	Thumb Interphalangeal
Metacarpophalangeal I	Metacarpophalangeal II	Metacarpophalangeal III	Metacarpophalangeal IV
Metacarpophalangeal V	Proximal Interphalangeal II hand	Proximal Interphalangeal III hand	Proximal Interphalangeal IV hand
Proximal Interphalangeal V hand	Knee		

To calculate observed DAS28 scores, the observed component value will be calculated first. Then the components will be included in the calculation per the DAS28 formula. If any observed component is missing in a window, then the observed DAS28 score will be missing.

9.4.7 Clinical Disease Activity Index (CDAI)

CDAI is a composite continuous index to assess disease activity without using hsCRP measurement.

It can be calculated based on TJC28, SJC28, Patient's Global Assessment of Disease Activity (PtGA) (in cm, 0 – 10) and Physician's Global Assessment of Disease Activity (PhGA) (in cm, 0 – 10).

$$\text{CDAI} = \text{TJC28} + \text{SJC28} + \text{PtGA (cm)} + \text{PhGA (cm)}.$$

To calculate observed CDAI scores, the observed component value will be calculated first. Then the components will be included in the calculation per the CDAI formula selected. If any observed component is missing in a window, then the observed CDAI score will be missing.

9.4.8 Simplified Disease Activity Index (SDAI)

SDAI is a composite continuous index to assess disease activity based on TJC28, SJC28, Patient's Global Assessment of Disease Activity (PtGA) (in cm, 0 – 10), Physician's

Global Assessment of Disease Activity (PhGA) (in cm, 0 – 10) and hsCRP (mg/dL). It can be derived as follows:

$$\text{SDAI} = \text{TJC28} + \text{SJC28} + \text{PtGA (cm)} + \text{PhGA (cm)} + \text{hsCRP (mg/dL)}.$$

To calculate observed SDAI scores, the observed component value will be calculated first. Then the components will be included in the calculation per the SDAI formula selected. If any observed component is missing in a window, then the observed SDAI score will be missing.

9.4.9 Clinical Remission (CR) and Low Disease Activity (LDA)

Clinical remission (CR) and low disease activity (LDA) based on DAS28 (CRP) and CDAI are defined as follows:

Disease Status	DAS28 [CRP]	CDAI
LDA	≤ 3.2	≤ 10
CR	< 2.6	≤ 2.8

9.4.10 Disability Index of Health Assessment Questionnaire (HAQ-DI)

HAQ-DI is a self-reported patient outcome measurement. It is calculated as the mean of the scores from 8 following categories with a range 0 – 3: Dressing and Grooming, Rising, Eating, Walking, Hygiene, Reach, Grip, and Activities. The higher the score, the more likely to associate with morbidity and mortality for the RA patient.

The maximum score for all the questions in each category is considered as the score for the category. The Standard disability index (HAQ DI) takes into account the subject's use of aids or devices or assistance in the scoring algorithm for a disability category. For each of the eight disability categories there is an AIDS OR DEVICES companion variable(s) that is used to record the type of assistance, if any, a subject uses for his/her usual activities. If aids or devices and/or assistance from another person are checked for a disability category, the score for this category is set to 2 (much difficulty), if the original

score is 0 (no difficulty) or 1 (some difficulty). The HAQ DI is then calculated by summing the adjusted categories scores and dividing by the number of categories answered. The HAQ DI cannot be calculated if the patient does not have scores for at least 6 categories.

Minimum clinically important difference in HAQ-DI is defined as change from Baseline ≤ -0.22 .

